4.5.5 Classification of investigator reported bleeding

Bleedings will be adjudicated by an independent CEC. To compare the investigator reported bleeding with the adjudicated bleeding an investigator reported bleeding classification is needed.

4.5.5.1 ISTH Major Bleeding, ISTH Clinically Relevant Non-Major and ISTH Minor Bleeding

A bleeding will be counted as investigator reported ISTH major bleeding if:

- 1. The outcome of the bleeding is fatal and/or
- 2. The bleeding is symptomatic and site is in a critical area or organ, i.e. bleeding site is: intracranial, intraocular, intraspinal, pericardial, retroperitoneal, intraarticular, or intramuscular with compartment syndrome and/or
- 3. The bleeding is clinically overt
 - a. with a recent decrease in the hemoglobin level of ≥ 2 g/dl within 48 hours of bleeding event, that was related to the bleeding event and/or
 - b. leading to transfusion of 2 or more unites of packed red blood cells or whole blood.

A bleeding will be counted as investigator reported ISTH Clinically Relevant non-major bleeding if it is considered any sign or symptom of hemorrhage, but does not fit the ISTH definition of major bleeding but does meet at least one of the following criteria:

- 1. requiring any healthcare professional guided treatment to control the bleeding
- 2. leading to hospitalization or increased level of care
- 3. prompting a face to face (i.e. not just a telephone or electronic communication) evaluation

A bleeding is considered any sign or symptom of hemorrhage, if the bleeding is overt, i.e. visible or documented by imaging.

An increased level of care is similar to the requirement 3., i.e. prompting a face to face (i.e. not just a telephone or electronic communication) evaluation

An overt bleeding that does not met the criteria for either ISTH major or clinically relevant non-major bleeding will be classified as ISTH minor bleeding.

4.5.5.2 TIMI Bleeding Definitions

The non-CABG-related TIMI clinically significant bleeding definition encompasses the following bleeding types excluding events that are related to a CABG procedure: TIMI Major bleeding, TIMI Minor bleeding and TIMI Bleeding requiring medical attention.

A bleeding will be counted as non-CABG related TIMI Major bleeding if

1. it is not related to a CABG procedure and

- 2. is any symptomatic intracranial hemorrhage and/or
- 3. has clinically overt signs of hemorrhage (including imaging) associated with a drop in hemoglobin of ≥ 5 g/dl (or when hemoglobin concentration is not available, an absolute drop in hemocrit of $\geq 15\%$) and/or
- 4. is fatal (bleeding leading to death within 7 days).

A bleeding will be counted as non-CABG related TIMI Minor bleeding if

- 1. it is not related to a CABG procedure and
- 2. has clinically overt signs of hemorrhage (including imaging) associated with a fall in hemoglobin of 3 to < 5 g/dl (or when hemoglobin concentration is not available, a fall in hemocrit of 10 to < 15%.

A bleeding will be counted as non-CABG related TIMI Bleeding event requiring medical attention if

- 1. it is not related to a CABG procedure and
- 2. requires medical treatment, surgical treatment, or laboratory evaluation and
- 3. does not meet criteria for major or minor bleeding event.

A bleeding will be counted as non-CABG mininal TIMI Bleeding event if

- 1. it is an overt bleeding and
- 2. does not meet criteria for major or minor TIMI Bleedign event or a TIMI Bleeding event requiring medical attention.

A bleeding is related to a CABG procedure if the site of bleeding is Cardiovascular system – CABG related.

In addition to TIMI significant bleeding also TIMI major bleeding and TIMI minor bleeding will be analyzed, i.e. adding bleeding events that fulfill all criteria of the respective bleeding but that are related to a CABG procedure.

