6.4.1.4 Exploratory Safety Analyses

Exploratory safety endpoints are:

- TIMI clinically significant bleeding,
- TIMI major bleeding,
- TIMI minor bleeding,
- BARC bleeding definition type 2, 3, 5,
- BARC bleeding definition type 3, 5
- BARC bleeding definition type 1, 2, 3, 5, and.
- BARC bleeding definition type 1.

For these endpoints the analyses follow the the estimations for the other bleeding. Descriptive tables of crude incidences of investigator-reported bleeding will be shown for all bleeding scales (ISTH, TIMI, BARC). A table will compare adjudicated and investigatorreported bleeding outcomes.

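### The derived TIMI bleeding classes in SAP 4.5.5.2 are not mutually exclusive, and the minimal class labelled non-CABG has no non-CABG criterion

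*SAP*

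**What the plan says.** SAP 4.5.5 sets up a classification of investigator-reported bleeding so that it can be compared with the adjudicated one. SAP 4.5.5.2 defines the TIMI part:

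- **Major:** unrelated to CABG, plus at least one of three routes. One route is an overt bleed with a hemoglobin drop of at least 5 g/dl (hematocrit 15% if hemoglobin is missing). The other two do not depend on hemoglobin: symptomatic intracranial bleeding ("is any symptomatic intracranial hemorrhage and/or") and fatal outcome ("is fatal (bleeding leading to death within 7 days").
- **Minor:** introduced by "A bleeding will be counted as non-CABG related TIMI Minor bleeding if", with two criteria only. The bleed is unrelated to CABG, and it is overt and "associated with a fall in hemoglobin of 3 to < 5 g/dl" (hematocrit 10 to <15% if hemoglobin is missing).
- **Requiring medical attention:** unrelated to CABG, needs treatment or laboratory work-up, and "does not meet criteria for major or minor bleeding event".
- **Minimal:** introduced by "A bleeding will be counted as non-CABG mininal TIMI Bleeding event if", with two criteria only. The bleed is overt, and it "does not meet criteria for major or minor TIMI Bleedign event or a TIMI Bleeding event requiring medical attention".

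The last paragraph of the section adds versions of major and minor that also take in CABG-related bleeds. The section does not say which class applies when a bleed meets two.

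The classes feed SAP 6.4.1.4: "Descriptive tables of crude incidences of investigator-reported bleeding will be shown for all bleeding scales (ISTH, TIMI, BARC". A further table there sets adjudicated against investigator-reported outcomes.

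**The concern.** There are two gaps in the criteria.

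1. Minimal is the only one of the four classes without a criterion on CABG, although its label says non-CABG. As a residual class it collects whatever the other three reject, and they reject CABG-related bleeds at their first criterion.
2. Medical attention and minimal both exclude the classes above them, but minor does not exclude major. Because major can be reached without any hemoglobin criterion, the two can be met together.

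The SAP writes such exclusions elsewhere. ISTH clinically relevant non-major and minor (4.5.5.1) and BARC type 2 (4.5.5.3) each exclude the more severe classes. The omission from TIMI minor therefore looks like a slip rather than a convention. The minimal definition was added only in SAP version 2.0 (section 7).

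A table that compares two classifications needs one class per bleed. Programmed as written, a severe bleed could appear in two classes, or in the mildest one, and the mismatch with adjudication could come from the derivation alone.

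**Working it through.** The SAP gives no figure to reproduce. The check is one of logic: write the criteria as rules and apply them to every kind of overt bleed they distinguish.

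**Inputs (all from SAP 4.5.5.2).** CABG-related (yes/no), symptomatic intracranial (yes/no), fatal (yes/no), hemoglobin fall (<3, 3 to <5, ≥5 g/dl), needs medical attention (yes/no). That gives 2 × 2 × 2 × 3 × 2 = 48 profiles, 24 with CABG and 24 without. They are logical cases, not expected frequencies. The CABG criterion is taken to govern all three routes to major.

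**Rules.**
- Major = not CABG, and (intracranial, or fall ≥5, or fatal)
- Minor = not CABG, and fall 3 to <5
- Medical attention = not CABG, needs attention, not major, not minor
- Minimal = overt, and not major, not minor, not medical attention

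**Two readings of the exclusion in minimal.** Under reading A, major and minor mean the non-CABG classes defined just above. Under reading B, they mean the CABG-inclusive versions of the section's last paragraph.

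**Major and minor together.** This needs intracranial and/or fatal (3 combinations) with a fall of 3 to <5 (1 level) and either value of medical attention (2). So 3 × 1 × 2 = 6 of 24 non-CABG profiles, under either reading. The hemoglobin route to major (≥5) cannot overlap with minor (<5). Dropping the CABG criterion, as the last paragraph does, gives the same 6 of 24 among CABG profiles in the CABG-inclusive classes.

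**CABG bleeds classed as non-CABG minimal.** The CABG profiles that meet no size, site or outcome criterion for major or minor are those not intracranial, not fatal and with a fall <3: 1 × 1 × 1 × 2 = 2. The other 24 − 2 = 22 meet at least one such criterion.

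| | Reading A | Reading B |
|---|---|---|
| CABG profiles that become minimal | 24 of 24 | 2 of 24 |
| of these, meeting size, site or outcome criteria for major or minor | 22 | 0 |

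Under reading B, one of the two remaining profiles needs medical attention and is still filed as minimal, because the CABG criterion keeps it out of the medical-attention class. The label contradicts the criteria under both readings; only the extent differs.

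**After correction.** With minor excluding major and minimal restricted to non-CABG bleeds, no profile falls in two of the four classes, no CABG profile is minimal, and each of the 24 non-CABG profiles falls in exactly one class. That result covers the non-CABG classes. The 6 CABG profiles that overlap in the CABG-inclusive major and minor are resolved only if the same precedence is stated there too.

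**The case against.** The strongest reply is that this is a wording slip with little consequence. Its parts stand to different degrees.

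- *The label already limits minimal to non-CABG bleeds.* A careful programmer may well honour it. But the other three classes carry the same label or intent and still list the criterion, so the numbered criteria of minimal remain incomplete.
- *The exclusion clause speaks of TIMI major and minor without the non-CABG qualifier, as the last paragraph does for the CABG-inclusive classes.* This is a plausible reading. A reader might infer that a CABG bleed of any size, even a fatal one, always ends up as minimal. The text does not support that: it holds under reading A only. Small CABG bleeds enter under both readings.
- *Major and minor are separate endpoints and need not partition the bleeds.* That is fair for the incidence tables, less so for a class-by-class comparison. A reader might also infer that major bleeds in general count as minor. They do not; only fatal or symptomatic intracranial bleeds with the intermediate fall do.
- *Nothing that is analysed for inference changes.* This stands. SAP 4.1 makes adjudication the basis of the final analysis, and TIMI minimal is not a listed endpoint.
- *Disagreement with the committee is not shown.* This also stands. Its definitions are in a charter that is not at hand, so disagreement caused by the derivation is possible, not certain.

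**Conclusion.** The point holds as a minor correction. The derived TIMI classes are not mutually exclusive, and one contradicts its own label. CABG-related bleeds can enter the non-CABG minimal class: small ones on either reading, large or fatal ones only if the exclusion refers to the non-CABG classes. An overt fatal or symptomatic intracranial bleed with a hemoglobin fall of 3 to <5 g/dl, or the hematocrit equivalent, meets both major and minor.

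The effect is confined to the descriptive investigator-reported TIMI tables, in particular the separate count for minor, and to the comparison with adjudication. It would be wrong to conclude that the adjudicated TIMI endpoints are distorted. Nor does the major/minor overlap change the participant-level TIMI clinically significant composite, since a bleed counted in either class is already in the union. The SAP gives no expected number of such bleeds; that they will be few is a judgement based on how narrow the conditions are.

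**What to change.** Make two changes to SAP 4.5.5.2, and the same in the derivation program:

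1. Give TIMI minimal the same opening criterion as the other three classes, that the bleed is unrelated to a CABG procedure.
2. State that each bleed is assigned only to the most severe TIMI class whose criteria it meets, so that minor excludes major. Say that this applies both to the non-CABG classes and to the CABG-inclusive major and minor of the last paragraph. Adding a not-major condition to non-CABG minor alone would leave the CABG-inclusive overlap in place.

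The cost is about two lines of text and code. One consequence should be accepted knowingly: a CABG-related bleed that is neither major nor minor then has no TIMI class, so the comparison table should show such bleeds on a line of their own.

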4.5.5.3 BARC Bleeding Definition

In this study the BARC bleeding definitions will be used. For that, different types are defined.

A bleeding will be counted as BARC bleeding Type 1 if it

1. is not actionable and does not cause the participant to seek any unscheduled performance of studies, hospitalization, or treatment by a healthcare professional.

A bleeding be counted as BARC bleeding Type 2 if it

- 1. has any overt, actionable sign of hemorrhage and
- 2. does not fit the criteria for type 3 or 5 and
- 3. requires non-surgical, medical intervention by healthcare professional and/or
- 4. leads to hospitalization or increased level of care and/or
- 5. prompts evaluation.

A bleeding "prompts evaluation" if it leads to diagnostic testing (laboratory or imaging).

BARC bleeding Type 3 subdivides in types 3a, 3b and 3c.

A bleeding will be counted as BARC bleeding Type 3a if it

- 1. is an overt bleeding with a hemoglobin drop of 3 to <5 g/dL and/or
- 2. any transfusion with overt bleeding is related to the bleeding.

A bleeding will be counted as BARC bleeding Type 3b if it

- 1. is an overt bleeding with a hemoglobin drop of \geq 5 g/dL and/or
- 2. is cardiac tamponade and/or
- 3. requires surgical intervention for control (excluding dental/nasal/skin/hemorrhoid) and/or
- 4. requires intravenous vasoactive agents.

A bleeding will be counted as BARC bleeding Type 3c if it

- 1. is intracranial hemorrhage (does not include microbleeds or hemorrhagic transformation, includes intraspinal), subcategories confirmed by autopsy or imaging or lumbar puncture and/or
- 2. intraocular bleeding compromising vision

The hemoglobin drop can be corrected for transfusion. 1 U of packed red blood cells or whole blood equals 1g/Dl hemoglobin.

BARC bleeding Type 5 are fatal bleedings. They subdivide into Type 5a and Type 5b.

A bleeding will be counted as BARC bleeding Type 5a if it

1. is probable fatal, i.e. no autopsy or imaging confirmation is done but it is clinically suspicious.

A bleeding will be counted as BARC bleeding Type 5b if it

1. is definite fatal, i.e. it is overt or autopsy or imaging confirmation has been done.

4.5.6 Blind Review of important deviations and validity findings

The results of the final data assessment will be documented in the final list of important deviations, validity findings and assignment to analysis set(s). Any changes to the statistical analysis prompted by the results of the review of study data will be documented in an amendment and, if applicable, in a supplement to this SAP.

5. Analysis Sets

5.1 Assignment of analysis sets

Final decisions regarding the assignment of subjects to analysis sets will be made during the review of study data before data base closure and documented in the final list of important deviations, validity findings and assignment to analysis set(s).

Full analysis set (FAS)

A subject will be included in the FAS if he/she is randomized to a treatment group.

Safety analysis set (SAF)

A subject will be included in the SAF if he/she is randomized to a treatment group and has taken at least one unit of the study medication.

Pharmacokinetic Analysis Set

A subject will be included in the pharmacokinetic analysis set, if it has received active treatment, has at least 1 valid plasma concentration of BAY 2433334 and is without protocol deviation, which would interfere with the evaluation of the PK data.

Pharmacodynamic Analysis Set

A subject will be included in the pharmacodynamic analysis set, has at least 1 valid pharmacodynamic value and is without protocol deviation, which would interfere with the evaluation of the pharmacodynamic data. All PD analyses will be performed on the PD analysis set (PDS).

6. Statistical Methodology

The primary analysis population for all analyses will be the SAF. Tables will be shown by treatment arm and overall. No adjustment for multiplicity will be performed.

6.1 **Population characteristics**

6.1.1 Disposition

The following will be tabulated by treatment group and overall:

- Study sample sizes by region and country
- Study sample sizes by country and site
- Participants disposition
- Number of participants and primary reasons for screening failures
- Number of participants and primary reasons for premature discontinuation of study medication
- Number of participants and primary reasons for premature discontinuation of study follow up.

Incidences for permanent discontinuation of the double-blinded study drug and of the followup period will be provided by randomized study treatment groups, based on the case report form data.

Kaplan-Meier estimates will be used to present

- time to the date of last double-blind dose of study treatment,
- time to the date of last follow-up contact,

all calculated as days from randomization, by study treatment group.

Other details regarding visit adherence (e.g., visit completed in person, by telephone, through third party) and completion as well as study drug adherence collected via CRFs will be summarized using frequency tables by visit and study treatment group.

6.1.2 **Protocol Deviations**

No per protocol analysis set will be defined in this study. The number of participants with major protocol deviations and validity findings according to the CRF will be summarized by study treatment group as well as reasons.

6.1.3 Demography and baseline characteristics

Demographic and baseline data as collected in the CRF will be evaluated descriptively for the SAF as well for the FAS, by treatment groups and overall. No statistical tests will be performed to compare these characteristics across treatment groups.

Descriptive statistics (such as mean, standard deviation, median, quartiles, minimum and maximum) will be provided for continuous variables.

Counts and (appropriate) percentages will be provided for categorical variables.

Besides others the following variables will be displayed:

- Sex
- Race (White, Black, Asian, other)
- Region (North America; Western Europe and Australia; Eastern Europe; Asia)
- Age (< 65 years, 65 75 years, > 75 years)
- BMI: $< 25; \ge 25 \text{ to } < 30; \ge 30 \text{kg/m}^2$
- Weight: <60; 60-90; >90 kg
- eGFR: <50; 50-80; >80 mL/min
- AF pattern: Paroxysmal, Persistent, Long-standing persistent, Permanent
- For patients currently treated with a NOAC the following subgroups will be defined
 - History of a prior bleed within the last 12 months requiring medical attention (yes/no)
 - Moderate renal dysfunction with eGFR 30-50 ml/min (yes/no)
 - \circ Current clinically indicated antiplatelet therapy with ASA ≤ 100 mg (yes/no)
- Stroke or TIA prior to enrollment (yes/no)
- Time from AF diagnosis to randomization: \leq 30 days; 30 days to 3 months; > 3months
- Chronic Kidney Disease (yes/no)
- Coronary Artery Disease (yes/no)
- Hypertension (yes/no)
- Diabetes (yes/no)
- Tobacco use: Never; Former; Current

6.1.4 Medical history

Medical history data will be evaluated by frequency tables, showing the number and percentage of participants with medical history findings (i.e., previous diagnoses, diseases or surgeries) that started before signing of the informed consent and that are considered relevant for the participant's study eligibility using MedDRA Primary System Organ Class / Preferred Term. Number and percentages of subjects with AF pattern will be shown separately.

6.1.5 **Prior and concomitant medication**

Prior and concomitant medication will be evaluated by frequency tables, showing the number and percentage of participants with

• prior medication, i.e. medications taken before start of study drug, regardless of when they ended,

- concomitant medication, i.e. medications taken within the treatment period
- ongoing concomitant medication at start of study drug,
- medication started during the treatment period, and
- medication started after stop of study medication.

Prior and concomitant medication will be shown by ATC classes and subclasses.

Separate tables will be provided for anticoagulants, antiplatelet therapy used and for CYP3A4 inhibitors and inducers.

A separate table for concomitant prohibited medication will be shown.

6.1.6 Subgroup analyses

Selected demography and baseline characteristics, medical history and prior and concomitant medication tables will be repeated for the following subgroups:

- Prior use of NOAC (yes/no)
- Risk factors for apixaban dosage (0-1, 2-3) •

6.2 Efficacy

Efficacy analyses in this study will be exploratory only.

Exploratory endpoints for this study are:

- the composite as well as individual components of CV death, MI, ischemic stroke, • and systemic embolism,
- all-cause mortality. •

Events will be counted in the intention-to-treat data scope for the full analysis set.

The number of participants with an efficacy endpoint and percentages will be shown by treatment arm.

Taking the time under risk into account, the exposure-adjusted incidence rate will be calculated for each treatment arm with an 90% confidence interval.

The incidence rate (IR) will be expressed as "participants with an event per 100 participant years". For that the following formula (Unkel, et al. 2019) is used:

$$IR = \frac{\# Participants with an event}{\sum time \ to \ event \ (or \ censoring)(in \ days)/(100 * 365.25)}$$

The 90% confidence interval for the IR will be computed as

$$\left[\frac{IR * \chi^2(0.05; 2e)}{2e}; \frac{IR * \chi^2(0.95; 2e)}{2e}\right],$$

with $\chi^2(q; 2e)$ the q quantile of a chi square distribution with 2e degrees of freedoms and e the number of participants with an event. (Nelson 1982)

In addition, time-to-first-event analyses taking competing events into account will be performed. For that Aalen-Johansen estimates for the cause specific cumulative risk will be presented.

The competing event for the efficacy events is death or non-CV death for endpoints that include CV death. There will be no competing event for all-cause mortality.

The cumulative incidence, i.e. the probability of having a specific event E at or before a timepoint t, $P(T \le t, E = 1)$, will be estimated for time-to-event endpoints by Aalen-Johansen estimators with the competing event as defined before. For the Aalen-Johansen estimator the cumulative hazard calculated by the cause-specific Nelson-Aalen estimator is needed. The calculation of the estimators follows Allignol, Beyersmann and Schmoor (Allignol, Beyersmann and Schmoor 2016).

The cause-specific Nelson-Aalen estimator for an event E at timepoint t is calculated as:

$$\hat{\Lambda}_E(t) = \sum_{t_j \le t} \frac{\#Participants \text{ with an event } E \text{ at } t_j}{\#Participants \text{ under risk at } t_j}.$$

The Aalen-Johansen estimator takes the difference of the cause-specific Nelson-Aalen estimator into account, weighted with the Kaplan-Meier (KM) survival function, i.e. the Aalen-Johansen estimator for time t is defined as:

$$\widehat{AJ_E}(t) = \sum_{t_j \leq t} \widehat{S}(t_{j-1}) (\widehat{\Lambda}_E(t_j) - \widehat{\Lambda}_E(t_{j-1})).$$

Gray's (Gray 1988) test for equivalence of the cumulative incidence functions, stratified by prior usage of NOAC, will be performed. To derive the Aalen-Johansen estimators and the test statistics with the corresponding confidence intervals, SAS program code corresponding to the following will be used:

```
PROC LIFETEST DATA = <dataset> ALPHA=0.1 ERROR=AALEN;
STRATA stratumn / GROUP=trtgrpn;
TIME ttevalue * status(0)/eventcode=1;
RUN;
/*
where
dataset = name of sub-dataset including all FAS participants randomized to
respective BAY2433334 treatment group and control group
trtgrpn = variable coding randomized antithrombotic treatment group
(0 = apixaban control group, 1 = BAY243334 treatment
ttevalue = time to first occurrence of outcome event or competing event
status = status of the participant at event time (0 = right-censored,
1 = event of interest, 2 = competing event)
stratumn = variable for NOAC stratification factor (two levels)
*/
```

Cause-specific HRs will be calculated for the respective event and the competing event. The cause-specific hazard ratios and the corresponding confidence intervals will be estimated on separate cause-specific hazard models for the comparison of the pooled doses of BAY 2433334 versus apixaban and for each treatment dose of BAY 2433334 versus apixaban (if applicable). No comparison of the different doses of BAY 2433334 is planned.

To derive the cause specific hazard ratios and the corresponding confidence intervals, SAS program code corresponding to the following will be used:

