The cumulative incidence risk, i.e. the probability of having a specific event E at or before a timepoint t, $P(T \le t, E = 1)$, will be estimated for time-to-event endpoints by Aalen-Johansen estimators with the competing event as defined in section 6.2.

The difference of the Aalen-Johansen estimators at day 85 (week 12) between BAY 2433334 treatment and Apixaban will be presented with a 90% confidence interval.

As the Aalen-Johansen estimator is approximately normal distributed (Aalen, Borgan and Gjessing 2008), the difference of Aalen-Johansen estimators is approximately normal distributed. Thus, the two-sided 90% confidence interval is obtained via:

Page: 21 of 25:

$$\left[(\widehat{A}J^{BAY}(85) - \widehat{A}J^{Apixaban}(85)) \pm z_{0.95} \sqrt{\sigma^2(\widehat{A}J^{BAY}(85)) + \sigma^2(\widehat{A}J^{BAY}(85))} \right]$$

with $\widehat{AJ}^{TRT}(85)$ the Aalen-Johansen estimator for treatment TRT at day 85, $z_{0.95}$ the 95% quantile of the standard normal distribution and $\sigma^2(\widehat{AJ}^{TRT}(85))$ the estimated variance of the Aalen-Johansen estimator at day 85, estimated with the Aalen method.

All analyses will be done for the pooled doses of BAY 2433334 and for each of the two doses.

csHRs will be calculated for the respective event and the competing event. Gray's test of equivalence of the cumulative incidence functions, stratified by prior usage of NOAC, will be performed. The cause specific hazard ratios and the corresponding confidence intervals will be estimated on separate models for the pooled doses of BAY 2433334 and each comparison (if applicable). No comparison of the different doses of BAY 2433334 is planned.

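### The LIFETEST call in SAP 6.2 suits the NOAC-stratified Gray test but does not give the per-arm Aalen-Johansen estimates it is also said to derive

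*SAP*

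**What the plan says.** Section 6.2 introduces its code with the words "To derive the Aalen-Johansen estimators and the test statistics with the corresponding confidence intervals, SAS program code corresponding to the following will be used". One call therefore has to supply the estimates, their intervals and the test.

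The call contains "STRATA stratumn / GROUP=trtgrpn" and "TIME ttevalue * status(0)/eventcode=1". The comments under it define the variables: "stratumn = variable for NOAC stratification factor (two levels" and "trtgrpn = variable coding randomized antithrombotic treatment group", the latter coded 0 for apixaban and 1 for BAY 2433334. The input is described as "dataset = name of sub-dataset including all FAS participants randomized to" one BAY 2433334 group or control. The options set a 10% alpha and the Aalen variance, and both of these serve the estimates.

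Stratification is mentioned in the text only for Gray's test: "test for equivalence of the cumulative incidence functions, stratified by prior usage of NOAC, will be performed". The Nelson-Aalen and Aalen-Johansen formulas in 6.2 have no stratum index.

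Section 6.4.1.2 then plans, for the primary safety endpoint, "The difference of the Aalen-Johansen estimators at day 85 (week 12) between BAY 2433334 treatment and Apixaban" with a 90% interval. The estimator and its variance are indexed by treatment alone. That section shows no Aalen-Johansen code of its own.

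**The concern.** A stratified test and an arm-level curve need different set-ups. In a stratified Gray test, treatments are compared within NOAC levels and the comparisons are combined. An arm-level cumulative incidence uses everyone in the arm, whatever their prior NOAC use. With the NOAC factor in STRATA and treatment in GROUP=, estimation is split by both factors, so the call returns no whole-arm curve and no whole-arm variance.

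A programmer who follows the printed code must then choose between reporting stratum curves, averaging them in some way, or writing a further call. The SAP does not fix that choice. The first option, and an unweighted average, would report something other than the quantity the text defines, with standard errors that do not belong to it.

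**Working it through.** The SAP states no numerical result on this point, so there is nothing to reproduce. The check is a comparison of code and text, followed by an illustration.

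**Code against text**

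| Item | Level | SAP section |
|---|---|---|
| Curves from the printed call | NOAC level by treatment: 2 × 2 = 4 per comparison | 6.2 |
| Nelson-Aalen and Aalen-Johansen formulas | No stratum term | 6.2 |
| Day-85 estimator and variance | Treatment only, 2 values and 1 difference | 6.4.1.2 |
| Minimum-event rule | 3 events, counted by treatment arm | 4.5.3 |
| Secondary bleeding estimates | Arms with 3 or more events | 6.4.1.3 |
| General display | By randomized arm | 4.1 |

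Every textual reference is to the arm. The SAP has no rule for combining four curves into two, and no matching variance.

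**Illustration by simulation (all inputs assumed)**

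Inputs: 500 pooled BAY 2433334 and 250 apixaban participants; day-85 event risk on apixaban about 2% without and 6% with prior NOAC use, halved on BAY 2433334; competing risk about 10%; no random censoring before day 85. The SAP's own estimator, the sum of S(t_{j-1}) × [Λ_E(t_j) − Λ_E(t_{j-1})], was applied once by arm and once by NOAC level within arm. Each row below is one simulated data set.

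| NOAC share | Analysis | BAY | Apixaban | Difference |
|---|---|---|---|---|
| 50% | By arm | 0.0180 | 0.0480 | -0.0300 |
| 50% | No prior NOAC | 0.0078 | 0.0168 | -0.0090 |
| 50% | Prior NOAC | 0.0288 | 0.0763 | -0.0475 |
| 30% | By arm | 0.0160 | 0.0240 | -0.0080 |
| 30% | No prior NOAC | 0.0088 | 0.0000 | +0.0088 |
| 30% | Prior NOAC | 0.0314 | 0.0789 | -0.0475 |

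In the 30% data set the apixaban cell without prior NOAC use had no events, and that stratum's difference has the opposite sign to the arm-level one. The unweighted mean of the two stratum differences is (0.0088 − 0.0475)/2 = -0.0194, against -0.0080 by arm.

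Weighting by stratum size within arm recovers the arm value. For BAY at a 50% share, where the realised share was 0.486: 0.514 × 0.0078 + 0.486 × 0.0288 = 0.0180. With random censoring added, the agreement was within about 0.0001.

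**Standard errors (assumed)**

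With risk p = 0.02 and n = 250 in an arm, SE = √(0.02 × 0.98/250) = 0.885 percentage points. In a stratum with half the arm, n = 125, SE = 1.252 points, a ratio of 1.41. For stratum shares of 30% and 70%, the ratio is 1/√0.3 = 1.83 and 1/√0.7 = 1.20. These ratios hold for any subset of that size. They show only that a stratum interval cannot stand in for an arm interval.

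**The case against.** The strongest reply is that nobody could mistake the intended quantity. The formulas are unstratified, the day-85 estimator is indexed by treatment, and the event thresholds are per arm. Four printed curves do not fit a two-term difference, so the mismatch would show at once and would be unlikely to yield a silent wrong number. The SAP also promises only code that corresponds to what is printed, which leaves room for a second call. All of this stands, and it is why the point is minor. It does not make the printed call produce the estimates assigned to it.

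A reader might infer that the day-85 risk difference is left without any valid input. The SAP does not support that. The call is printed for exploratory efficacy on the FAS. Section 6.4.1.2 refers back to 6.2 for the competing-event definition and does not say that it reuses the call. The link is an inference from this being the only Aalen-Johansen code visible in the text, and other code blocks are evidently missing from the text as extracted.

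A reader might also take the day-85 difference for the main supportive analysis of the primary endpoint. The SAP lists it among several additional analyses and does not rank them.

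Finally, the reading of the call rests on the usual understanding of STRATA with GROUP= in this procedure; SAS was not run. The conclusion would fail only if the procedure disregarded the STRATA variable when it estimates the curves.

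**Conclusion.** The point holds as a minor error in the code specification. The call in 6.2 serves the stratified Gray test and does not deliver the arm-level Aalen-Johansen estimates and intervals that the same sentence assigns to it. For the exploratory efficacy estimates this follows directly from 6.2. For the day-85 difference in 6.4.1.2 it depends on the call being reused there.

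The primary crude incidence proportion ratio is untouched, no decision rule depends on these estimates, and the estimand is clear from the formulas. The size cannot be derived from the SAP. The simulated differences rest on assumed sample sizes, risks and NOAC shares, and show only that stratum and arm values can diverge, in one data set with opposite signs.

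**What to change.** 1. In 6.2, keep the printed call and label it as the code for the NOAC-stratified Gray test only.
2. Add a second call with the same PROC and TIME statements and `STRATA trtgrpn;`, without the NOAC factor. Name it as the source of the arm-level Aalen-Johansen estimates, their Aalen variances and the 90% confidence intervals. State that any unstratified test this call prints is not reported.
3. In 6.4.1.2, state that the day-85 difference takes its two estimates and variances from the second call, run on the SAF with the treatment emergent data scope.

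The cost is one short code block and two or three sentences. No data collection, sample size or primary analysis changes.
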